# 1.7 Current initiatives in Nepal

The University of British Columbia (UBC) Sickle Cell Project, a part of the UBC Global Health Initiative, aims to spread awareness of sickle cell disease and to help with screening patients in rural communities of Nepal, while collaborating with local non-profit organizations such as Creating Possibilities (CP) Nepal. CP Nepal has operated since 2006, with an overarching goal of protecting and advocating for the rights of marginalized women and children in Nepal. Since 2015, the UBC Sickle Cell Project have collaborated with CP Nepal, and sent teams of 6-12 medical students annually to conduct screening, diagnosis and education of SCD in the district of Dang, Nepal. So far, four sustainable health posts have been set up in rural parts of Western Nepal to screen for SCT and SCD.

In 2015/2016, a study conducted by the UBC Sickle Cell team and CP Nepal found the prevalence of SCD and SCT to be around 10% within the Tharu community in Dang, Nepal, based on screening approximately 3000 individuals aged 6 months to 40 years [43]. In some parts of Western Nepal, such as Nepalgunj, the prevalence was found to be as high as around 25% [11]. Since many of the studies in Nepal do not include newborn screening, the prevalence of the disease could be higher in rural communities of Nepal, and extensive screening and diagnosis programs are required to accurately identify and treat affected patients. The current study to evaluate performance of low-cost detection techniques is inspired by efforts of teams such as UBC Sickle Cell team and CP Nepal. The UBC Sickle Cell team and CP Nepal plan to help and support the Nepal study.

When the UBC Sickle Cell team conducted their initial study in 2015/2016, they focused on the sickling test for screening and had to send blood samples from some of the patients to India for confirmatory electrophoresis tests, since the gold standard HPLC tests were not available anywhere in Nepal. Over the last few years, some hospitals and clinics across Nepal have

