# 4.0 Objectives

Objectives specific to the current study are to:

- 1. Determine accuracy (sensitivity and specificity) of automated sickling test to detect HbS, compared to gold standard HPLC, and to conventional solubility test
- Determine whether SCD, SCT and healthy individuals can be classified using the automated sickling test that leverages machine learning on images of blood films under hypoxia
- Validate accuracy (>95% sensitivity and specificity) of lateral-flow assays (HemoTypeSC and Sickle SCAN) to detect SCD/SCT, and of Gazelle variant test to detect SCD, SCT, and β-thalassemia; and determine if low-cost techniques can potentially replace HPLC/electrophoresis tests in rural and remote settings

Long-term objectives of the overall project are to:

- 1. Implement trained machine learning algorithm to classify SCD, SCT and healthy individuals during screening tests in Nepal
- 2. Implement relevant low-cost point-of-care techniques in rural and remote communities of Nepal using insights and conclusions from current study

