## 6.3 Statistical Analysis Plan

Considering HPLC as the reference test, the sensitivity, specificity, positive predictive value (PPV) and negative predictive value (NPV) of the index tests or low-cost techniques (automated

sickling test, HbS solubility test, HemoTypeSC, Sickle SCAN, and Gazelle Hb variant test) will be evaluated.

For each case, the following definitions apply:

- True positive (TP): indicates a positive result for both the index test and the reference test
- True negative (TN): indicates a negative result for both the index test and the reference test
- False positive (FP): indicates a positive result for the index test, but a negative result for the reference test
- False negative (FN): indicates a negative result for the index test, but a positive result for the reference test

The following metrics will be calculated using the total number of TP, TN, FP, and FN:

Sensitivity = 
$$\frac{TP}{TP + FN} \times 100\%$$
  
Specificity =  $\frac{TN}{FP + TN} \times 100\%$   
 $PPV = \frac{TP}{TP + FP} \times 100\%$   
 $NPV = \frac{TN}{TN + FN} \times 100\%$ 

The metrics (sensitivity, specificity, PPV, and NPV) for the index tests will be calculated for the following two categories:

- 1. **Detection analysis by hemoglobin variant** (HbA, HbS, HbC, β-thalassemia): Heterozygous or homozygous forms containing a particular hemoglobin variant in both the index test and the reference test are true positive results for that variant. Test results lacking a particular hemoglobin variant in both index and reference tests, irrespective of other variants present, are true negative results for that variant. The following hemoglobin variants will be analyzed for the index tests.
  - HbS Solubility: HbA, HbS
  - Automated sickling: HbA, HbS
  - HemoTypeSC: HbA, HbS, HbC
  - Sickle SCAN: HbA. HbS. HbC
  - Gazelle Hb Variant: HbA, HbS, HbC, β-thalassemia
- 2. **Detection analysis by phenotype**: In this analysis, the metrics for homozygous and heterozygous states will be calculated differently. The following phenotypes will be analyzed for the index tests.
  - Automated sickling: HbAA, HbAS, HbSS, Overall
  - HemoTypeSC: HbAA, HbAS, HbSS, (HbAC, HbSC, HbCC), Overall
  - Sickle SCAN: HbAA, HbAS, HbSS, (HbAC, HbSC, HbCC), Overall
  - Gazelle Hb Variant: HbAA, HbAS, HbSS, HbS/β-thalassemia, HbA/β-thalassemia, Hbβ/β-thalassemia, (HbAC, HbSC, HbCC), Overall

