  - HbS Solubility: Not applicable, since solubility test can only identify the hemoglobin variant but not the homozygosity or heterozygosity

Any data that is excluded from the analysis, due to indeterminate results, missing data, withdrawal of consent, or any other reason, will be reported.

A total of around 120 participants – around 20 individuals with SCD (HbSS), 20 individuals with SCT (HbAS), 20 individuals with sickle cell /  $\beta$ -thalassemia compound heterozygous form (HbS/ $\beta$ -thalassemia), 20 individuals with  $\beta$ -thalassemia (Hb $\beta$ / $\beta$ -thalassemia), 20 individuals with  $\beta$ -thalassemia trait or carrier form (HbA/ $\beta$ -thalassemia), and 20 healthy individual participants (HbAA) – will be recruited for the study.

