### 7.2 Inclusion and Exclusion Criteria

#### 7.2.1 Inclusion Criteria

Since the techniques evaluated in the study aims at detecting sickle cell disease (SCD), sickle cell trait (SCT), and  $\beta$ -thalassemia, the following number of participants will be included in the study:

- 20 individuals with SCD (HbSS)
- 20 individuals with SCT (HbAS)
- 20 individuals with sickle cell/β-thalassemia compound heterozygous form (HbS/β-thalassemia)
- 20 individuals with β-thalassemia (Hbβ/β-thalassemia)
- 20 individuals with β-thalassemia trait or carrier form (HbA/β-thalassemia)
- 20 healthy individual participants or normal participants (HbAA, participants without any known hemoglobin disorders, such as SCD, SCT or β-thalassemia)

Participants older than 1 year of age at the time of drawing blood will be eligible. Signed and dated consent or assent forms will be required by the participants or their parents/guardians.

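### Section 6.3 pools every variant-negative participant, so each specificity is an average weighted by the recruitment quotas; report it by comparison group as well

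*Combined protocol and SAP*

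**What the plan says.** Section 6.3 computes specificity from summed true negatives and false positives, with HPLC as reference. In the analysis by hemoglobin variant, results that lack the variant on both tests, "irrespective of other variants present, are true negative results for that variant". In the analysis by phenotype, the section says only that the metrics for homozygous and heterozygous states are worked out differently. It does not define who counts as a negative. Gazelle gets phenotype rows that include HbAA and HbA/β-thalassemia. The solubility test gets none. No confidence interval and no breakdown of specificity by comparison group is planned.

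Sections 6.3 and 7.2.1 fix the sample by quota: "A total of around 120 participants", in six groups of 20 (HbSS, HbAS, HbS/β, Hbβ/β, HbA/β and "20 healthy individual participants or normal participants").

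The third study-specific objective in section 4.0 reads "Validate accuracy (>95% sensitivity and specificity) of lateral-flow assays (HemoTypeSC and Sickle SCAN) to detect SCD/SCT". It extends the same target to Gazelle for SCD, SCT and β-thalassemia, and then asks whether low-cost tests could replace HPLC or electrophoresis in rural and remote settings. As background, section 1.7 reports a 2015/2016 study that "found the prevalence of SCD and SCT to be around 10% within the Tharu community in Dang, Nepal", and about 25% in some parts of Western Nepal.

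**The concern.** A pooled specificity is a weighted mean of the specificities in the groups that make up the negatives. Here the investigators' quotas set those weights, not the population to be screened. The contrast that decides carrier screening is HbAA against HbA/β, and sections 1.4 and 1.8 stress that asymptomatic carriers matter. Healthy people nevertheless supply only a third of the β-thalassemia negatives. For HbS the imbalance runs the other way, because β-thalassemia samples supply two-thirds of the negatives.

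A single pooled figure set beside >95% could therefore mislead in either direction. It could look reassuring while a tenth of healthy participants are miscalled. It could also look poor because of reactions in β-thalassemia samples only. A reader weighing replacement of HPLC needs to know which of these happened.

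**Working it through.** **Inputs.** Six groups of 20 (sections 6.3 and 7.2.1); the pooling rule (6.3); the >95% target (4.0), read as a point estimate because no interval rule is given. HPLC is assumed to confirm the recorded group.

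**The plan's own total.** 6 × 20 = 120, which reproduces the stated figure. The documents give no precision or power target behind it.

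**Who the negatives are.**
- β-thalassemia, variant row: HbAA + HbAS + HbSS = 60; healthy share 20/60 = 33.3%.
- HbS, variant row: HbAA + HbA/β + Hbβ/β = 60; β-thalassemia share 40/60 = 66.7%.
- HbA/β phenotype row: undefined. If taken as one phenotype against the rest, 120 − 20 = 100; healthy share 20/100 = 20%.

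**Most false positives (FP) that still exceed 95%.** Specificity = (N − FP)/N.
- Variant row, N = 60: FP = 2 gives 58/60 = 96.7%. FP = 3 gives 57/60 = 95.0%, which is not above 95%. If both false positives are HbAA, 2/20 = 10% of healthy people are miscalled. Specificity in HbAA is then 18/20 = 90.0% (exact 95% CI 68.3 to 98.8%).
- HbA/β phenotype row under the one-against-rest assumption, N = 100: FP = 4 gives 96/100 = 96.0%, and FP = 5 gives 95.0%. If all four are HbAA, 4/20 = 20% are miscalled (specificity in HbAA 80.0%, exact 95% CI 56.3 to 94.3%). The same four calls in the variant row give 56/60 = 93.3%, which is below the target.

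**How likely a misleading pooled figure is.** If the true false-call rate is 10% in HbAA and zero elsewhere, the variant row exceeds 95% when at most 2 of 20 are miscalled: P(Bin(20, 0.10) ≤ 2) = 67.7%. With a 1% rate in the other 40 negatives it is 56.5%. At a true 20% in HbAA the two figures are 20.6% and 15.7%.

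**Opposite direction, HbS.** Suppose specificity is 100% in HbAA and 90% in both β-thalassemia groups: (20 × 1.00 + 40 × 0.90)/60 = 56/60 = 93.3%. The pooled value is below 95% with no error in healthy people.

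**Group size.** The SAP says around 20. The largest tolerated healthy miscall rate in the variant row is 2/18 = 11.1% with 18 per group and 3/22 = 13.6% with 22.

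**The case against.** Several points on the other side stand.

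- **The miscalls would not be hidden.** The sensitivity of the Gazelle HbAA phenotype row is the share of healthy people called HbAA, so 2 or 4 miscalls would show there as 90% or 80%. What remains is that section 4.0 does not tie the >95% figure to that row, and that the solubility test has no such row.
- **The examples are constructed.** Nothing in the documents shows that Gazelle's errors cluster in healthy samples, or that an HbS test reacts in β-thalassemia samples. At 18/20 the interval includes 95%, so the data could not show that the healthy-group rate misses the target.
- **There is no formal pass/fail rule.** The primary endpoint in section 5.0 is descriptive, and the first hypothesis in section 3.0 uses overall accuracy above 90% for Gazelle. The risk lies in how the result is read.

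Three stronger readings are tempting but are not supported.

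- A reader might infer that Gazelle could meet the target while miscalling 20% of healthy people. That needs the unstated one-against-rest rule, and the same result falls short in the variant row.
- A reader might want the target applied to HbAA alone. With 20 people only 20/20 exceeds 95%, and its exact lower limit is 83.2%. A test with true specificity of 97% would reach it with probability 0.97^20 = 54%. For HbS, that rule would also drop the β-thalassemia samples that the plan includes on purpose.
- A reader might re-weight to a community mix, for example HbAA as 75 to 90% of negatives, giving 1 − 0.10 × (0.75 to 0.90) = 92.5 to 91%. No such mix is stated. It comes from subtracting the HbS prevalence and ignoring other forms, although section 1.4 puts β-thalassemia in 26 to 70% of Nepalese hemoglobinopathies.

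The >95% target also does not cover the solubility test, which is a comparator in the first objective.

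**Conclusion.** The concern holds as a matter of analysis and reporting. The pooled specificity in section 6.3 is tied to the quota mix and should not stand alone as a field value. In the worst case, the β-thalassemia variant row can exceed 95% (96.7%) with 10% of healthy participants miscalled. The HbS row can fall to 93.3% with none miscalled.

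The group composition in the variant rows follows directly from the plan. The sizes rest on assumptions about where errors fall and on reading >95% as a point estimate. The documents do not support saying that the plan conceals the error, that a 20% miscall rate would meet the target overall, or that quota sampling is itself the fault. The fault is pooling across the quotas without also showing the parts.

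**What to change.** In section 6.3:

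1. Define the negatives for each phenotype row.
2. Report specificity for each test and target by comparison group with exact 95% intervals. For β-thalassemia the groups are HbAA, HbAS and HbSS. For HbS they are HbAA, HbA/β and Hbβ/β, with the solubility test as a descriptive row.
3. Keep the pooled specificity, labelled as specific to the quota mix.
4. State which row the >95% figure in section 4.0 applies to. Do not attach it to the 20 HbAA participants alone.
5. Base any statement on rural replacement on the group-specific results as well as the pooled value.
6. Treat any re-weighting to a community mix as an optional sensitivity analysis, with its assumed range stated.

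The cost is SAP wording and a few table rows from data already being collected, with no new participants or tests. The drawback is wide intervals at about 20 per group.

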#### 1.2 Thalassemia and its interaction with sickle cell disease

Hemoglobin is the protein in red blood cells that transports oxygen (and carbon dioxide) between lungs and other tissues/cells in the body. The hemoglobin molecule is made up 4 polypeptide chains or subunits, such as alpha, beta, gamma or delta chains. The three most common types of hemoglobin are hemoglobin A (normal adult hemoglobin), hemoglobin F (fetal hemoglobin), and hemoglobin A2 (normally found in small quantities in adults). Hemoglobin A is

made up of 2 alpha chains and 2 beta chains ( $\alpha_2\beta_2$ ). Hemoglobin F is made up of 2 alpha chains and 2 gamma chains ( $\alpha_2\gamma_2$ ). Hemoglobin A2 is made up of 2 alpha chains and 2 delta chains ( $\alpha_2\delta_2$ ).

Thalassemia is an inherited condition which results in a deficiency or abnormality in the synthesis of one or more of these polypeptide/globin chains or subunits. Clinical symptoms include anemia resulting from inadequate hemoglobin synthesis, and ineffective production of red blood cells due to an unbalanced accumulation of one of the globin chains.  $\alpha$ -thalassemia is caused by mutations in the alpha globin genes. Since each chromosome normally has 2 alpha genes, there are four possible syndromes related to  $\alpha$ -thalassemia with increasing severity caused due to 1 to 4 genes being absent or failing to function: 1)  $\alpha^+$  thalassemia trait, 2)  $\alpha^0$  thalassemia trait, 3) hemoglobin H disease, and 4) hemoglobin Bart's hydrops fetalis.  $\beta$ -thalassemia is caused by mutations in the beta globin genes. Although there are more than 400 mutations identified, the majority of cases either result in a reduced ( $\beta^+$ ) or absent ( $\beta^0$ ) production of beta chains. Based on the clinical severity, thalassemia is also classified as thalassemia minor or trait (where individuals are silent carriers and asymptomatic), thalassemia intermedia (associated with mild anemia and is transfusion independent), and thalassemia major (associated with anemia and is transfusion dependent) [2].

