## 1.5 Conventional screening and diagnosis

The following techniques have been commonly used to detect hemoglobin S (HbS) related to SCD or SCT.

**Sickling test**: The presence of hemoglobin S can be demonstrated in a sickling test, where red blood cells change their shape from round bi-concave shape to sickled shape, under conditions of hypoxia or deoxygenation. When a drop of blood is sealed (using petroleum jelly/paraffin wax mixture or nail lacquer) between a glass slide and a cover slip, the metabolic activity of white blood cells causes deoxygenation, which induces sickling after a few hours, if HbS is present. The deoxygenation can be accelerated by adding a reducing agent such as sodium metabisulphite or sodium dithionite. Sickling can be induced using a reducing agent within 30 minutes to an hour for SCD and SCT, and the changes in morphology of red blood cells can be observed under a microscope, to distinguish SCD and SCT individuals from healthy participants [2], [13]. The sensitivity of the sickling test ranges from 65% [14] to 97.3% [15] and the specificity ranges from 96% [14] to 99.6% [15]. The sickling test, which is relatively inexpensive, was predominantly used as a screening test for HbS, but has mostly been replaced by the solubility test.

**HbS solubility test**: The solubility test relies on the principle that hemoglobin S, when deoxygenated, is insoluble in a high molarity phosphate buffer, which forms crystals that refract light and causes the solution to turn turbid [2]. Sickle solubility tests provide positive results for cases of SCD and SCT beyond early infancy – for early infancy (infants less than 6 months) the percentage of HbS can be below 20%, which could result in false negative tests [13]. The sickle solubility test, whether positive, negative or ambiguous, should be followed up by a confirmatory test, such as hemoglobin electrophoresis. The follow up tests are required to confirm the presence of HbS, distinguish SCT from SCD, or identify false negative cases due to low HbS concentration or technical error [13]. For rapid results or for emergency cases, the sickle solubility test can be combined with a blood count and a blood film analysis to distinguish SCT from SCD with reasonable accuracy. The sensitivity of the solubility test ranges from 45% [14] to 99% [15] and the specificity ranges from 90% [14] to 99.9% [15].

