# 3.0 Hypothesis

We hypothesize that

1. Gazelle diagnostic device can detect  $\beta$ -thalassemia and SCD/SCT with an overall accuracy greater than 90%, compared with HPLC as the reference test

- 2. an automated sickling test (standard sickling test enhanced using low-cost microscopy and machine learning) has a higher overall accuracy than conventional screening techniques (solubility and sickling tests) to detect hemoglobin S in blood samples
- 3. the automated sickling test can additionally classify SCD, SCT and healthy individuals with a sensitivity greater than 90%, based on morphology changes of red blood cells, unlike conventional sickling or solubility tests that do not distinguish between SCD and SCT cases

Overall, we hypothesize that an assessment of the performance and accuracies of low-cost point-of-care techniques (automated sickling test, solubility test, lateral-flow assays, Gazelle Hb variant test) against HPLC tests will provide researchers and health workers with feasible alternative options for screening and detecting SCD, SCT and  $\beta$ -thalassemia in a variety of situations based on the needs of the communities and the resources available.

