#### Manual observation under microscope

- Examine slide under microscope (20x objective, 10x eyepiece)
- Identify as positive sickling test (SCD or SCT) if greater than 25% of the red blood cells appear sickled or deformed (Figure 1 shows sickling in an SCT individual)

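### Two HbS-dependent tests, automated sickling and HbS solubility, are scored for HbA, so their HbA accuracy would depend on case mix and an unstated reading rule

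*Combined protocol and SAP*

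**What the plan says.** Section 6.3 computes sensitivity, specificity, PPV and NPV against HPLC, by variant and by phenotype. By variant, the entry for the low-cost microscopy test is "Automated sickling: HbA, HbS", and the line above it names the same two variants for HbS solubility. By phenotype, the entry is "Automated sickling: HbAA, HbAS, HbSS, Overall". Solubility is left out of the phenotype analysis because it cannot tell homozygous from heterozygous blood.

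The scoring rules are general. A variant-level true negative is defined by "Test results lacking a particular hemoglobin variant in both index and reference tests, irrespective of other variants present". A false positive "indicates a positive result for the index test, but a negative result for the reference test".

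On what the sickling reaction shows, section 1.5 says "The presence of hemoglobin S can be demonstrated in a sickling test". The manual read-out in section 7.5.1 is "Identify as positive sickling test (SCD or SCT) if greater than 25% of the red blood cells appear sickled or deformed"; no HbA result is defined there. The automated version is meant to go further: hypothesis 3 in section 3.0 expects it to "classify SCD, SCT and healthy individuals with a sensitivity greater than 90%, based on morphology changes of red blood cells".

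Sections 6.3 and 7.2.1 plan six groups of about 20: HbSS, HbAS, HbS/β-thalassemia, Hbβ/β-thalassemia, HbA/β-thalassemia and HbAA. Section 1.2 describes HbA as "made up of 2 alpha chains and 2 beta chains", and says that β-thalassemia mutations may reduce beta-chain production or abolish it.

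**The concern.** A person whose beta-chain production is wholly absent makes no HbA. If that person also carries no HbS, the blood does not sickle. None of the three phenotypes listed for automated sickling lacks both HbA and HbS, so such a participant has no correct listed result. The SAP neither says how an HbA call is derived from the images nor says what happens to these samples.

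For solubility the gap is wider. A turbid tube shows that HbS is present, whether or not HbA is present too, so a positive result cannot be turned into an HbA call.

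Sensitivity and specificity of these techniques are the primary outcome (section 5.0). HbA rows for these two tests would sit in the same table as those for HemoTypeSC and Sickle SCAN, which section 1.6 says detect HbA. A low HbA specificity for automated sickling could then be taken as poor slide reading or a poor network, when it came from who was enrolled and how a negative was scored.

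**Working it through.** **Sample size.** The plan's only related figure is the total: 6 × 20 = 120, which agrees with section 6.3. It states no precision, power or target for HbA specificity of either test.

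**Inputs.** From section 7.2.1: 20 HbSS, 20 HbS/β-thalassemia and 20 Hbβ/β-thalassemia participants. Not given, so taken as assumptions from 0 to 20:
- s = HbS/β participants with no HbA on HPLC
- b = Hbβ/β participants with no HbA on HPLC

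**What each listed output does to a sample with neither HbA nor HbS**
- HbAA: false positive for HbA, true negative for HbS.
- HbSS: true negative for HbA, false positive for HbS.
- HbAS: false positive for both.

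Reading the slide correctly (no sickling, so no HbS) leads most naturally to HbAA.

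**Ceiling on HbA specificity for automated sickling.** Assume that every non-sickling sample is output as HbAA, that every HbA-free sample with HbS is correctly output as HbSS, and that all participants are scored. Then TN = 20 + s and FP = b, and

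specificity = TN/(TN + FP) = (20 + s)/(20 + s + b).

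| | s = 0 | s = 10 | s = 20 |
|---|---|---|---|
| b = 0 | 20/20 = 100% | 30/30 = 100% | 40/40 = 100% |
| b = 5 | 20/25 = 80.0% | 30/35 = 85.7% | 40/45 = 88.9% |
| b = 10 | 20/30 = 66.7% | 30/40 = 75.0% | 40/50 = 80.0% |
| b = 20 | 20/40 = 50.0% | 30/50 = 60.0% | 40/60 = 66.7% |

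Small numbers already matter: b = 2 with s = 0 gives 20/22 = 90.9%, and b = 3 with s = 20 gives 40/43 = 93.0%.

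**Solubility.** Suppose clear means HbA present, and try both possible rules for turbid.
- Turbid also means HbA present: every sample is called HbA-positive, TN = 0, and specificity is 0%.
- Turbid means HbA absent: the 20 HbAS participants and the 20 − s HbS/β participants who have HbA become false negatives. The reference HbA-positives number 20 HbAA + 20 HbAS + 20 HbA/β + (20 − s) + (20 − b) = 100 − s − b, of which 60 − b are called positive. At s = b = 0, sensitivity is at most 60/100 = 60%; at s = b = 20 it is at most 40/60 = 66.7%.

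Neither rule gives a usable HbA result, and the plan states neither.

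**HbS scoring only.** HbS-positive: HbSS + HbAS + HbS/β = 60. HbS-negative: Hbβ/β + HbA/β + HbAA = 60. No ceiling is built in. If HbA is kept for automated sickling only among HbS-positive participants, the HbA-negative denominator is 20 + s (20 to 40) and the ceiling is 100%.

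**The case against.** The strongest reply is that the ceiling is not in the plan. Section 6.3 lists phenotypes to be analyzed, not the network's output classes. Section 7.8 trains the network on hemoglobin phenotype, with HPLC as ground truth, and does not fix the classes. A network might learn a separate thalassemia class, or samples might be set aside as indeterminate, which section 6.3 allows if reported. This stands. A reader might infer that the false positives arise by construction and that the formula is a hard upper bound. The documents do not support that: the HbAA reading is an inference, and a network that wrongly called such a sample HbSS would score it correctly for HbA at the cost of an HbS error.

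A reader might also infer that HbA scoring has no basis at all for automated sickling. That goes too far. Sections 1.6 and 3.0 expect morphology to separate SCT from SCD, which gives a route to an HbA call in HbS-positive blood. The gap is confined to non-sickling samples.

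The size depends on b. Section 1.2 allows reduced rather than absent beta chains, so some or all Hbβ/β participants may have HbA. Section 1.2 also describes thalassemia major as transfusion dependent, and section 7.2.2 excludes anyone transfused within 3 months, which may lower b. At b = 0 there is no ceiling.

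The counts assume that all participants are scored. Section 7.8 keeps only about 10% of images for testing; if accuracy is reported on that set, its own counts replace those above.

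Finally, failing to recognise absent HbA in non-sickling blood is a real limit of the test in this population and could fairly be reported. It should then be reported as that, and not left inside an unlabelled specificity.

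**Conclusion.** The point holds in a limited form. Two tests that react to HbS are scored for HbA without a rule for making the call. For automated sickling, if non-sickling is read as HbAA, HbA specificity cannot exceed a figure between 50% and 100%, set by the unstated numbers of HbA-free participants in the HbS/β and Hbβ/β groups. For solubility the objection is stronger and does not depend on that split: by the SAP's own account the test cannot separate HbAS from HbSS, so a positive result gives no HbA call.

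It would be tempting to conclude that a main claim of the study is biased. The documents do not support that. Hypothesis 2 and objective 1 concern HbS, hypothesis 3 concerns classification into SCD, SCT and healthy, and the >95% goal in section 4.0 covers the lateral-flow assays and the Gazelle test. No formal HbA comparison between automated sickling and the lateral-flow assays is planned. What is affected is the meaning of the HbA rows for two tests in the primary accuracy table. This is a minor point, but worth correcting before analysis.

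**What to change.** In the variant list of section 6.3, remove HbA from the entries for HbS solubility and automated sickling, and score both on HbS only.

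If HbA is kept for automated sickling:
- state the rule that turns network output into an HbA call;
- report HbA metrics only among participants who are HbS-positive on HPLC, and label them so;
- report separately how the HbS-negative Hbβ/β samples were classified.

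The cost is a few words of SAP text. No extra participants or tests are needed. The downside is that an HbA row is lost for solubility and lost or restricted for automated sickling; no hypothesis uses either row.
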